2.8 Study Hypotheses

A regimen of 8 Gy X 3 over 5 days (every other day) is as safe (well tolerated) and effective as 6 Gy X 5 over five consecutive days.

3.0 RESEARCH RISK & BENEFITS

3.1 **Risk of Study treatment**

The risks involved in using the treatment machine or the CT scanning are described as possible fatigue, skin damage, swelling, muscle tightness, and position-induced muscle aches (back and shoulder).

3.2 **Other Risks of Study Participation**

Additional risks to study participation include breach of confidentiality. Privacy protection procedures are in place and good clinical practice guidelines are followed throughout the study to minimize the risks associated with breach of confidentiality.

3.3 **Potential Benefits**

The potential benefits to subjects with study participation are improved overall survival. The information obtained from this research may help others with this disease in the future.

3.4 Drug Information

NA

4.0 Staging Criteria

TNM Stage I, T1 N0 M0 breast cancer patients. TNM Stage 0, TisNxM0 breast cancer patients.

5.0 **RESEARCH POPULATION**

Patient Eligibility

284 study subjects at least over the age of 50-90 female are to be entered into this study across all NYU School of Medicine and Bellevue Hospital (satellite campus). This study will be an outpatient study. We do not plan to enroll vulnerable population and there are no restrictions on race/ethnicity.

Inclusion criteria:

5.1	Post-menopausal women defined as either1) at least 2 years without menstrual period or2) patients at least 50 years or older with serological evidence of post-menopausal status or
	3) hysterectomized patients of any age with FSH confirmation of post-menopausal status.
5.2	 pT1 breast cancer, excised with negative margins. Low risk-pTis breast cancer, excised with negative margins. Criteria for low risk-pTis: Screen-detected Low to intermediate puelleer grade

- Low to intermediate nuclear grade
- \leq 2.5cm in size
- Resected with negative margins at \geq 3mm)
- 5.3 clinically N0 or pN0 including sentinel node negative

Exclusion criteria:

- 5.4 Previous radiation therapy to the ipsilateral breast.
- 5.5 Presence of a proportion of DCIS in the core biopsy specimen which is compatible with extensive intraductal component (EIC).

5.6 Subject Recruitment, Registration and Screening

All efforts will be made to actively recruit and retain members of minority groups in this study. The inclusion and exclusion criteria in this study should not have a negative effect on the enrollment of these populations.

Target enrollment for this study is 284 patients. Each cohort will consist of 142 patients. Patients will be recruited from physicians at the NYU Perlmutter Cancer Center and Bellevue Hospital. Consenting, screening, and treatment takes place at the NYU PCC under the supervision of the Principal Investigator. Prospective subjects receive detailed information about this study its investigational nature, required study procedures, alternative treatments, risks and potential benefits of the study. They also receive the informed consent document to read. All questions are answered by the PI and qualified research personnel.

The Principal Investigator will:

- 1. Obtain signed and dated informed consent from the potential patient before ant study specific procedures are performed.
- 2. Determine patient eligibility See Sections 5.1 through 5.5.
- 3. Submit registration to NYU Perlmutter Cancer Center CTO
- 4. Receive registration confirmation from the Research Coordinator at NYU Perlmutter Cancer Center CTO, including a unique study identification number assigned to the patient by the research coordinator, which will be distributed to the study team upon registration.

Recruitment and consenting will take place in a private area such as an exam room to protect the patient's privacy. The informed consent process and documentation follows the established procedures of the NYU PCC CTO.

5.7 Informed Consent

Consent will be obtained only by a participating investigator who has completed requisite training for human subject research and has been instructed by the Principal Investigator about the patients and address any questions or concerns prior to obtaining written informed consent for participation and HIPAA authorization.

Patients will be given adequate time to read the consent form. They will be given time to ask questions about the study in private exam rooms. Questions will be answered by a participating physician, or qualified research study team member all of whom have completed requisite training for human subject research. Investigators will review the informed consent form with patients and address any questions or concerns prior to obtaining written informed consent for participation. Investigators will stress that participation in the study is completely voluntary and will not affect the care patients receive or result in any loss of benefits to which patients are otherwise entitled.

For non-English speaking patients, institutional translation services will be utilized. For these patients the consent letter and all other information will be administered orally and a witness, not related to the research project, will be present while the oral presentation is given. A short form will be utilized for the subject to sign in his/her name and the translator and/or witness must sign the short form. The translator will also sign the main consent form.

For patients who cannot read. A witness, not related to the research study will be present. The consent will be read to the patient. The patient will also be allowed to ask any questions s/he may have. The investigator will ask the patient questions to ensure s/he understands the study. If the

investigator determines the subject understands the study, the patient will mark an X where his/her name would go and the witness will sign the consent form.

5.8 Documentation of Consent

The Principal Investigator or IRB approved sub-investigator will be responsible for documentation in the medical record that consent has been obtained from all participants. A signed copy of the consent form will be given to each participant. Original consent forms will be stored in the subject's medical chart.

6.0 **REGISTRATION GUIDELINES**

Patients will be registered with the Clinical Investigations Support Office of the department of Radiation Oncology and with the Clinical Research Office of the Cancer Center.

- 6.1 At the time of registration, one signed and dated informed consent will be obtained, along with three copies for patient, medical record, Clinical Investigations Support Office of the department of Radiation Oncology and with the Clinical Research Office of the Cancer Center.
- 6.2 At the time of registration, the eligibility registration worksheet will be completed.
- 6.3 A flow sheet to record baseline characteristics including demographic and disease characteristics will be used to collect data as well as detailing clinical parameters and toxicity. The flow sheets will be maintained during therapy and the entire duration of the study (5 years).
- 6.4 Confidentiality

All data and medical information obtained once a patient has decided to participate in this research, will be kept confidential to the extent permitted by law and will not be released without the patient's written permission except as described in this paragraph. The study information will be recorded on study report forms. In all study forms, patients will be identified only by their initials and patient number. Patient names will not be reported in any publication; only the data obtained as a result of their participation in this study will be made public.

All patients will be required to sign a written informed consent prior to being registered on this study. Every effort will be made to answer questions raised by patients and their families or advocates regarding the protocol and alternative therapies prior to asking a patient to sign the consent form.

Once eligibility is verified, a unique patient study number will be issued within 24 hours of receiving all required registration material. The patient will not be identified by name. This is the point, at which, the patient is considered on study. Subjects must not start any protocol procedures prior to registration.

6.5 Screening Process

During the screening visit, the following will happen:

- 1. The study doctor will ask the subject questions about their medical history, including information about other medical problems.
- 2. You will be asked what prescription medications, over-the-counter (OTC) supplements, herbal products, vitamins, and any other OTC products you are taking.
- 3. The study doctor will perform a physical examination and collect your vital signs (heart rate, breathing rate, blood pressure and temperature).

6.6 Selection Process

If subject is eligible to participate in this study, the subject is randomly assigned to one of two radiation treatment groups:

Group 1 (Arm 1): will receive a radiation dose of 6Gy each day for 5 consecutive days.

Group 2 (Arm 2): will receive a radiation dose of 8Gy every other day over a period of 5 days.

Before starting radiotherapy, you will be required to undergo a radiation therapy planning session/simulation session to enable your radiation doctor to carefully design the radiation treatment so that only the area that is affected by tumor is radiated while trying to avoid surrounding normal tissue. A simulation session is required to obtain images of your chest to tailor the radiation treatment to your body shape. During this simulation session, you will lie prone (on your belly) so that we can best cover the radiation target region (the tumor bed) while avoiding heart and lung tissue as much as possible. The tumor bed is where your tumor was before you had it surgically removed.

6.7 Early Withdrawal of Subjects

A subject has the right to voluntarily discontinue treatment or withdraw from the study at any time, for any reason, and without repercussion. The investigator has the right to discontinue a subject from the study or withdraw a subject at any time.

Reasons for subject withdrawal from the study may include:

- Subject withdrawal of consent at any time
- Any medical condition that the investigator determines my jeopardize the patient's safety if she continues in the study or continues treatment.
- The investigator determines it is in the best interest of the patient
- Failure of subjects to adhere to protocol requirements

Every effort will be made to obtain information on subjects who withdraw from the study, including the reason for taking a participant off the study. The date the participant was removed, must be documented.

6.8 Follow-up

After the end of radiation treatment, each subject will be followed for 30 days (± 2 weeks), at 90 days and 6 months (± 6 weeks) for serious adverse event reporting. Assessments will continue with yearly (± 8 weeks) visits for the remaining 5 years.

7.0 METHODS & PROCEDURES

7.1 Descriptive Factors/Stratification/Randomization Scheme

This is a prospective, randomized study. No stratification is planned. The study schema describes the study design.

7.2 Randomization Scheme

Research Coordinators will randomize patients to one of the 2 arm of the study, as soon as they have provided informed consent and eligibility packet to participate in the research study. The randomization list will be done via REDCap, a browser-based, metadata-driven EDC software solution for research databases and will be maintained in the department of Radiation Oncology.

Eligibility	 284 stage I or low risk-stage 0 breast cancer in post-menopausal women, s/p segmental mastectomy Low risk-stage 0 criteria: Screen-detected Low to intermediate nuclear grade ≤ 2.5cm in size Resected with negative margins at ≥3mm
Day 0	Informed consent and randomization CT planning for determination of tumor bed on the prone position
Day 1-5 (start within 90 days from last breast surgery)	Daily IGRT, IMRT or Conformal Partial breast irradiation, randomly assigned to:

Table 5 Study Schema

600 cGy X 5 fractions, over 5 consecutive days (arm 1) or 800 cGy X 3 fractions, every other day, over 5 days (arm 2)

8.0 RATIONALE FOR STUDY DESIGN

- 8.1 The women in this study will receive either 5 or 3 radiation fractions to the tumor bed. We have chosen to study T1 or low risk-Tis post menopausal women because in this subset: 1) the tumor is small enough to be treated by partial breast radiation 2) the odds of having multicentric disease are low, making it ethical to avoid whole breast irradiation, 3) the most benefit from reducing the radiation schedule from 5 to 3 could be expected.
- 8.2 The Principal Investigator explains all elements of the protocol to the patients and answers any and all questions. Clinical procedures are performed by the principal investigator. The consent process takes place in the Department of Radiation Oncology at NYU Medical Center.
- 8.3 Once the process of eligibility has been determined, patients will be randomly assigned to one of the 2 arms:
 Arm 1: 6 GyX5 over 5 days, on five consecutive days
 Arm 2: 8 GyX3 over 5 days, every other day
- 8.4 Simulation and treatment will be started within 90 days from surgery, in order to maximize the chances of optimal lumpectomy cavity visualization on the planning and cone beam CT scans. Start of treatment within 60 days from surgery is encouraged, but the treating physician is allowed a window up to 90 days from last breast surgery to start the radiation treatment, as long as clinical judgment supports accurate visualization of the target lumpectomy cavity at that timepoint.
- 8.5 All subjects will be followed for 30 days (± 2 weeks), at 90 days and 6 months (± 6 weeks), then yearly for 5 years (± 8 weeks) (see 11.0 Study calendar).

9.0 RADIATION THERAPY/TREATMENT PLAN

- 9.1 Radiation Dose Specification: The prescription dose is the dose delivered to a reference point within the clinical target volume. The prescription dose should cover at least ninety- five percent of the planning target volume.
- 9.2 Target Volumes:
 - 9.2.1 The resection cavity should be discernible based upon architectural changes in the breast tissue by the CT images and is defined as the clinical target volume (CTV).
 - 9.2.2 The planning target volume (PTV) = CTV + 1.5 cm margin.
 - 9.2.3 PTV eval = PTV limited to be within the defined ipsilateral breast tissue, specifically excluding the 1st 5 mm of tissue under the skin and tissue beyond the chest wall, pectoralis muscles and lung.

- 9.2.4 Whole breast reference volume: all tissue encompassed within traditional tangent field borders, excluding tissue deep to the chest wall interface and using the skin surface as the superficial border.
- 9.3 Imaging: A treatment planning CT of the breast will be acquired with the patient in the treatment position (prone), utilizing the same immobilization devices as will be used for treatment. CT scan thickness should be ≤ 0.375 cm through the tumor bed region. These images will be used in 3D treatment planning of the breast in accordance with the dose specification constraints.
- 9.4 Treatment Machine: A linear accelerator with > 4 MV x-rays is required.
- 9.5 Immobilization Techniques: Patients will be set-up for treatment and CT scanning utilizing a dedicated table designed to accommodate prone positioning for breast treatment [15].
- 9.6 Target Positioning Verification: Digitally acquired radiographic images, acquired prior to each fraction, will be used to verify the position of the target with respect to the treatment machine's isocenter using digitally reconstructed radiographs (DRRs) as a reference image set. Both kV and MV images may be used to verify setup.
- 9.7 IGRT Target Localization: Cone-beam CT (CBCT) images will be acquired prior to the first radiation treatment. By using IGRT to image the post-operative tumor bed of the breast in "real-time", the operator may automatically align the tumor bed with the treatment machine on the day of treatment. If shifts are made based upon the CBCT images, they will be recorded and the following day's portal images will be taken. If the resection cavity is not visualized then cone-beam CT images will be used to ensure optimal positioning of the breast tissue.
- 9.8 Treatment Planning: 3D-Conformal or Intensity Modulated Radiation Therapy (IMRT) treatment planning is allowed. This includes "field-in-field" beams as well as the use of dynamic multi-leaf collimator (MLC) derived using inverse planning or electronic compensator techniques. Field arrangements and technique should be chosen that satisfy the PTV_eval and normal tissue dose constraints using Dose-Volume Histogram (DVH) analysis. By carefully selecting the gantry and table angle combinations that do not enter or exit through other organs of the body, the dose can be confined to the traditional breast treatment volumes treated using a pair of tangent photon beams. No plan will be deemed acceptable if fields are directed towards the contralateral breast, heart or lung. Non-coplanar beam arrangements are encouraged, but not required. Dose calculations with tissue inhomogeneity correction must be used.
- 9.9 Normal Tissue Dose Constraints:

- 9.9.1 Uninvolved by tumor breast: Less than 60% of the whole ipsilateral breast should receive >50% of the prescription dose and less than 35% of the whole breast should receive the prescription dose.
- 9.9.2 Ipsilateral lung: Less than 15% of the lung can receive 30% of the prescribed dose.
- 9.9.3 Contralateral lung: Less than 15% of the lung can receive 5% of the prescribed dose.
- 9.9.4 Heart: Less than 5% of the heart can receive > 5% of the prescription dose.

10.0 TOXICITIES TO BE MONITORED AND DOSAGE MODIFICATIONS

- 10.1 Expected toxicities include fatigue and skin reactions within the radiation field. Erythema, dry and wet desquamation of the skin will be recorded weekly.
- 10.2 In the previous study of 45 patients there were no grade 2-3 skin toxicities[19]. Additional experience with the same regimen in 292 patients, demonstrated no grade 2-3 acute toxicity.
- 10.3 The risks involved in using the treatment machine or the CT scanning are described in the regular informed consent given to all patients undergoing radiation therapy.
- 10.4 The risks associated with venipuncture may occasionally include pain, bruising, fainting or a small infection at the puncture site.

11.0 STUDY CALENDAR

All subjects will be followed the first 30 days (± 2 weeks), at 90 days and 6 months (\pm 6 weeks) for serious adverse event reporting. Assessments will continue with yearly (\pm 8 weeks) visits for the remaining 5 years. Acute and late effects will be recorded following the criteria described in Appendix 1 and 2. At each post treatment follow-up visit, a physical exam to detect clinical recurrence will be performed. Mammographic studies and/or MRI will be performed and reviewed on an annual basis. The degree of fibrosis assessed by palpation will be measured as per Appendix 2, late effects.

Procedure Summary	Pre treatm ent	Day 1	Day 2	Day 3	Day 4	Day 5	30 days post treatme nt	Follow Up - 90 day post treatment	Follow Up 6 months post treatme nt	Follo w up - Every year for 5 years
Informed Consent	X									
MD/NP visit: physical and vital signs/cosmesis assessment (you will be examined for any skin changes at the radiation site) [§]	x	X §*		X§*		X _{8*}	x	x	x	x
Medical History	x						X*	X*	X*	X*
Mammogram	x								X**	X**
Lumpectomy Pathology Report	x									
Randomization (Treatment assignment)	x									
Treatment simulation***	x									
Baseline CBCT, first RT		x								
Port films/ each RT dose after the first one ^{a,b}			x	x	x	X				
Radiation Therapy		X ^{a,b}	Xa	X ^{a,b}	Xª	X ^{a,b}				
AEs		X	X	X	x	X	X	X	x	x

Table 6	Flow	Chart/Time	and Events	Schedule for	· Treatment and	Follow up
	1.10.00		and Evenus	Schedule 101	11 cauncine and	ronow up

[§]MD evaluation will occur at least once during treatment visits.

^{§*} MD evaluation will occur at least once if randomized to Arm 2

* first 30 days (± 2 weeks) post-treatment, then 90 days and 6 months (± 6 weeks), and then yearly for the next 5 years (± 8 weeks).

** Standard annual mammogram (or MRI) for both breasts.

*** May occur before Informed Consent, as this is part of standard of care

^aArm1 6Gy X 5 fractions (5 days)

^bArm2 8Gy X 3 fractions (3 days)

12.0 CRITERIA FOR EVALUATION AND ENDPOINT DEFINITIONS

- 12.1 Acute and late toxicity will be reported as scheduled in the above study calendar (10.1) following the criteria in Appendix 1.
- 12.2 Local recurrence will be classified as it follows:
 - 12.2.1. Local recurrence within the field of conformal radiation is defined as TRUE LOCAL RECURRENCE.
 - 12.2.2 In breast recurrence outside the treatment volume will be defined as LOCAL RECURRENCE OUTSIDE THE FIELD, SAME BREAST
 - 12.2.3 Axillary/ intra-mammary or supraclavicular recurrence in the same side of the index lesion will be defined as REGIONAL RECURRENCE /SAME BREAST.
- 12.3 At the time of local recurrence all patients will undergo disease assessment with CT of Chest/ Abdomen/ Pelvis and, if symptomatic, bone scan and/or brain MRI.

Local/regional recurrences will be further grouped as:

12.3.1 ISOLATED LOCAL/REGIONAL RECURRENCES

12.3.2. CONCOMITANT LOCAL/REGIONAL AND DISTANT RECURRENCES

Patients developing local recurrences after systemic recurrence has been documented will be classified as:

- 12.3.3. METACRONOUS LOCAL/REGIONAL RECURRENCES.
- 12.4 CONTRALATERAL BREAST CANCER will also be recorded and reported as invasive and noninvasive.

13.0 STATISTICAL AND DATA MANAGEMENT CONSIDERATIONS

Study Design: This study is a prospective randomized controlled trial to test the hypothesis that 8 Gy x 3 fractions is not worse that 6 Gy X 5 fractions, with respect to the development of breast fibrosis.

The current 6X5 schedule results in 1% 5 year recurrence rate and 10% of grade 2 or 3 fibrosis and approximately 32% of any induration or retraction, measured at after a minimum of 6 months from treatment. In other words approximately one out of 10 patients experience grade 2-3 fibrosis after lumpectomy and partial breast radiation.

Based on our prior experience, we observed a 10% rate of grade 2-3 fibrosis in these patients. With 142 patients randomized to each of the two treatment arms, we can test the hypothesis that the rate of fibrosis with 8Gy x3 is not more than 10% worse than the expected rate on the 6 Gy x 5 arm with one sided alpha =0.025 and power =80%. The trial will have a planned interim analysis when 142 patients across both arms are evaluable for fibrosis assessment at 2 years from accrual. Table 7 below provides the stopping boundaries for the interim analysis.

All analyses may be stratified by whether a ppatient started treatment within 60 days from surgery or within 90 days from surgery.

 Table 7 Stopping Boundaries for Non-inferiority with Respect to Proportion of Patients with

 Fibrosis Treated with 8Gy x3 Compared with Control of 6GY x5 Overall 1-sided alpha = 0.025,

 power =80%, O'Brien-Fleming Boundaries Calculations from EAST V 6.2, Cytel Inc.

 To Deject Us of Non-inferiority

		To Reject Ho of Non-inferiority				
Analysis	Number of Patients Randomized and Evaluable for Fibrosis	Critical Value of z-statistic	Alpha level	Difference in Proportion of Patients with Fibrosis (8Gy x3 -6Gyx5)		
Interim	142	≤-2.96	≤0.0015	≤-0.0493		
Final	284	≤-1.97	≤0.0245	≤0.0299		

Data management will be carried out by staff of the Department of Radiation Oncology and the NYUCI under the direction of Drs. [name] and [name]. Randomization will occur via REDCap (Research Electronic Data Capture), after consent is acquired, by the PI, research nurse, in the department of Radiation oncology. Data will be entered into Velos, a database management system maintained by the NYULMC PCC CTO according to the procedures of the NYULMC PCC CTO. Patients will be followed every 12 months to evaluate their status with respect to recurrence. Recurrences will be evaluated using standard criteria in the Dept. of Radiation Oncology that are provided in the protocol. Data will be transferred from the Velos database to the Division of Biostatistics for analysis. The Principal Investigator, Research Nurse, and Research Coordinators have access to data collected.

Analysis: Patient characteristics at randomization will be summarized by treatment group using descriptive statistics and graphical displays. For the primary endpoint of fibrosis, the proportions of patients by grade of fibrosis will be compared in the two treatment arms using contingency table methods and chi square tests. The primary analysis will be the difference in proportions of patients with grade 2 or 3 fibrosis between the two treatment groups compared using a non inferiority z- test. Secondary endpoints including rates of recurrence at 1, 2, and 3 years post randomization will be estimated with 95% confidence limits within treatment groups along with plots of Kaplan-Meier time to recurrence curves.

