14.1.2 DATA AND SAFETY MONITORING PLAN

This study will be monitored by the Data Safety Monitoring Committee (DSMC) of the New York University (NYU) Perlmutter Cancer Center (PCC). The DSMC operates based on the 2011 National Cancer Institute approved Charter. It is an existing and multidisciplinary committee (consisting of clinical investigators/oncologists, biostatisticians, nurses, and research administration staff knowledgeable of research methodology and design and in proper conduct of clinical trials) that is responsible for monitoring safety, conduct and compliance in accordance with protocol data monitoring plans for clinical trials conducted in the NYULMC Perlmutter Cancer Center that are not monitored by another institution or agency. The DSMC reports to the Director of the NYULMC PCC.

Per the NYU PCC Institutional Data Safety and Monitoring Plan, this study will be monitored by DSMC at least annually (from the date the first patient is enrolled), and at the completion of the study prior to study closure. This review includes accrual data, subject demographics and adverse events. The Principal Investigator is required to attend the review of their study. Additional reviews can be scheduled based on SAE reports, investigator identified issues, and external information, etc. The DSMC will review safety data every 6-8 weeks.

In accordance with HIPAA and associated privacy regulations, a patient's authorization to use personal identifiable health information may be required from each patient before commencement of research activities. This authorization document must clearly specify what parties will have access to a patient's personal health information, for what purpose and for what duration.

At the NYU Perlmutter Cancer Center, all investigator-initiated protocols are subject to a standardized data and safety monitoring, which includes scientific peer review, IRB review and DSMC review as well as internal auditing.

The review of AEs and trial conduct for this trial occurs at several levels:

(1) Principal Investigator: Adverse events are evaluated monthly by the principal investigator in conjunction with the research nurses, data manager and research team.

(2) DSMC, at least annually

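### The interim plan has a boundary only for less fibrosis on 8 Gy x 3: no pre-specified guideline covers excess fibrosis on that arm, and no by-arm fibrosis report to the DSMC is stated

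*Combined protocol and SAP*

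**What the plan says.** Grade 2-3 fibrosis is the primary endpoint. The protocol's section 13.0 specifies a "planned interim analysis when 142 patients across both arms are evaluable for fibrosis assessment at 2 years from accrual", followed by a final analysis at 284. Of the interim rule it says "Table 7 below provides the stopping boundaries for the interim analysis". Table 7 has one set of critical values. At the interim these are z ≤ -2.96, alpha 0.0015, and a difference (8 Gy x 3 minus 6 Gy x 5) of -0.0493 or lower. At the final they are z ≤ -1.97, alpha 0.0245, and a difference of +0.0299 or lower. A negative difference means less fibrosis on 8 Gy x 3.

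On DSMC review, section 14.1.2 says "This review includes accrual data, subject demographics and adverse events". Extra reviews may be called on SAE reports or issues that the investigator raises, and the investigator reviews adverse events monthly. Section 14.0 grades adverse events on Appendix 1, which covers acute reactions and has no fibrosis item. Section 11.0 grades fibrosis by palpation on Appendix 2 (LENT/SOMA). The DSMC is not named as recipient of the interim analysis.

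**The concern.** Fibrosis is the toxicity that the trial exists to measure, and section 2.7 warns that fractions above 2 Gy may raise its risk. The one comparative rule in the plan responds only when the shorter schedule looks better. If it looks worse, by any amount, Table 7 says nothing and the default is to carry on. A clear excess could then pass the interim with nobody required to consider it. The interim as written protects the non-inferiority claim. It gives no defined protection to patients still to be randomised to 8 Gy x 3.

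**Working it through.** **Inputs (section 13.0).** Design: "one sided alpha =0.025 and power =80"%. Control rate: "we observed a 10% rate of grade 2-3 fibrosis in these patients". Margin: the 8 Gy x 3 rate "is not more than 10% worse than the expected rate on the 6 Gy x 5 arm", taken as +10 percentage points. Size: "With 142 patients randomized to each of the two treatment arms". The interim has 142 evaluable patients, taken as 71 per arm (information fraction 0.5).

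**Step 1: reproduce the plan's figures.**
- Sample size per arm = (1.960 + 0.842)² × (0.1×0.9 + 0.1×0.9) / 0.10² = 7.85 × 0.18 / 0.01 ≈ 141.3, rounded up to 142. This matches.
- O'Brien-Fleming-type spending (Lan-DeMets) at half information gives z = 2.963 (alpha 0.0015), then z = 1.969 (alpha 0.0245). Both match.
- Boundary on the difference = 0.10 - z × √(0.18/n). Interim, n = 71: 0.10 - 2.963 × 0.0503 = -0.0492 (stated -0.0493). Final, n = 142: 0.10 - 1.969 × 0.0356 = +0.0299. Both match within rounding.

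The Table 7 numbers are sound. The gap is an omission.

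**Step 2: what the plan does at the interim if 8 Gy x 3 is worse.** Exact binomial, 71 per arm, 10% on 6 Gy x 5. An excess of at least 10 points needs 8 or more extra cases (7/71 = 9.9%, 8/71 = 11.3%).

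| True 8 Gy x 3 rate | Table 7 interim crossed (difference ≤ -0.0493) | Observed excess ≥ 10 points |
|---|---|---|
| 10% | 16% | 1.8% |
| 15% | 3.5% | 15.6% |
| 20% | 0.6% | 46% |
| 25% | 0.06% | 76% |
| 30% | 0.006% | 93% |

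Nothing in the plan attaches an action to the last column.

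**Step 3: an example.** Take 7/71 against 21/71, an excess of 14/71 = 19.7 points.
- Pooled rate 28/142 = 0.197; z for a difference above zero = 0.197 / √(0.197 × 0.803 × 2/71) = 2.95, one-sided p = 0.0016.
- Against the margin, z = +1.50. On the current trend the chance of still reaching z ≤ -1.97 at the final analysis is effectively zero.
- No stated boundary is crossed.

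**Step 4: cost of a 10-point guideline.** Simulated two-look trials with 10% on both arms, using Table 7's z values and unpooled variances, give power of 80.8% without the guideline and 80.6% if every trigger stopped the trial: about 0.2 points. (The normal approximation without the guideline gives 80.1%.) A rule that can only remove later claims of non-inferiority cannot raise the one-sided 0.025, and if it is non-binding Table 7 stands unchanged.

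**Step 5: who would still be protected at the interim.** The accrual rate r per month is not in the documents. Assuming steady accrual and no losses, enrolment when the 142nd patient reaches 2 years is min(284, 142 + 24r).

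| r per month (assumed) | Enrolled at interim | Still to enrol | Of these, to 8 Gy x 3 |
|---|---|---|---|
| 3 | 214 | 70 | 35 |
| 4 | 238 | 46 | 23 |
| 5 | 262 | 22 | 11 |
| 142/24 ≈ 5.9 or more | 284 | 0 | 0 |

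**The case against.** A reader might infer that harm on 8 Gy x 3 triggers nothing at all. The documents do not support that. Adverse events are recorded throughout, SAEs are reported within 24 hours, the investigator reviews events monthly, and the DSMC reviews safety data and can meet again when issues are raised. What is missing is narrower: a threshold and a stated comparison between arms.

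A reader might also infer that fibrosis is kept from the DSMC. That does not follow either. Section 14.0 defines an adverse event broadly enough to take in new fibrosis, section 11.0 records late effects on Appendix 2, the list of review content need not be exhaustive, and the DSMC works under a charter that is not in the documents. The most that can be said is that by-arm reporting of fibrosis is not stated.

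Nor should weight be put on section 14.1.2 giving both an annual minimum and "The DSMC will review safety data every 6-8 weeks". An annual minimum is a floor, so the two can coexist, and neither bears on the missing guideline.

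Two further objections have force. First, Table 7 is a non-inferiority boundary, so its failure to fire when 8 Gy x 3 is worse is correct behaviour. Table 2 also gives both schedules the same calculated fibrosis dose (120 Gy), so the plan did not expect an excess. This makes the point one of design choice, but it does not remove the need to say what happens if the expectation is wrong. Second, a 10-point trigger would sometimes fire when the true excess is inside the margin (15.6% at a true 15%), and by the interim there may be nobody left to protect. Both stand. They argue for a non-binding guideline and for earlier by-arm review.

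**Conclusion.** The point holds as an omission. Table 7 is numerically correct but runs in one direction. The plan contains no pre-specified harm or futility guideline for excess grade 2-3 fibrosis on 8 Gy x 3, and no statement that Appendix 2 fibrosis by arm reaches the DSMC. Where the true 8 Gy x 3 rate is 20% to 30%, an observed excess of at least the trial's own margin would be seen at the interim 46% to 93% of the time with no required response. These figures assume 10% on 6 Gy x 5, an even 71/71 split and complete 2-year assessment. How many patients an interim guideline would spare cannot be fixed, because accrual is not given; on assumed rates it runs from 35 allocations to 8 Gy x 3 down to none. This is a worthwhile, low-cost improvement to monitoring. It does not undermine the primary analysis.

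**What to change.** 1. **By-arm table (the more important part).** Add to the review content in section 14.1.2 a table seen only by the DSMC, at its scheduled reviews, giving by arm the worst Appendix 2 fibrosis grade from the 6-month visit onward and local recurrences in the section 12.2 categories. Six months is the minimum interval that section 13.0 uses for its historical rates. The data are those section 11.0 already asks for. Table 6 has no separate fibrosis row, so confirm that the grade is captured at each of these visits. The table needs no stopping threshold. The cost of repeated by-arm looks was not computed, so access should be confined to the DSMC.

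2. **Interim guideline.** Add to Table 7 a guideline marked non-binding, and name the DSMC as recipient of the interim. For example, an observed excess of 10 points or more on 8 Gy x 3 would send the by-arm data to the DSMC for a decision on whether enrolment continues. Ten points is the trial's own margin; another value could be chosen and its operating characteristics stated in the same way.

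**Cost.** Protocol wording and one extra table. State the downside openly: a review is triggered 1.8% of the time at equal 10% rates, 15.6% at a true 15% and 46% at a true 20%. About 0.2 points of power are lost at equal rates if the guideline is always followed. Sample size and Table 7's existing critical values stay as they are.
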